9 STATISTICAL ANALYSIS METHODS

9.1 Subject Disposition

The number of Screen Failures and reason for screen failure will be presented overall. A listing, grouped by stratum, will be provided that indicates the subject's date and time of randomization, randomized treatment assignment, randomization number, kit number(s), block number, randomized infection type, and prior antibiotic stratum (receipt of an allowed antibacterial therapy in the 72 hours prior to randomization - yes or no).

The number of subjects included in each of the analysis populations (ie, ITT, Safety, mITT, micro-mITT, CE-EOT, CE-PTE, ME-EOT and ME-PTE) will be summarized by treatment group. A table will summarize the reasons for exclusion from each population and a listing will be provided that indicates each subject's inclusion in/exclusion from the populations and the reason for exclusion from each of the populations.

A listing will be provided of randomized subjects who did not meet all inclusion/exclusion criteria, and which criteria were not met. The number and percentage of subjects completing the study (defined as receiving at least one dose of test article and returning for all of the EOT, PTE and FU visits), not completing the study, missing each of the EOT and PTE Visits, and prematurely discontinuing from test article will be presented for each treatment group and overall for the ITT, mITT, and CE-PTE populations (by definition, a subject in the CE-PTE population cannot have missed the PTE Visit, unless the subject was a clinical failure at the EOT Visit). Reasons for premature discontinuation of test article, not completing the study, and for missing each of the visits, as recorded on the eCRF will be summarized (number and percentage) by treatment group. Percentages of subjects discontinued from test article and not completing the study will be compared between treatment groups using Fisher's exact test. A listing of all subjects who prematurely discontinued from test article or not completing the study will be presented, and the primary reason for discontinuation of test article or not completing the study will be provided.

9.2 Demographics and Baseline Characteristics

Except where indicated, demographic data and baseline characteristics will be presented by treatment group for the Safety, mITT, micro-mITT, and CE-PTE populations. A table will present the subject demographics (eg, gender, age, ethnicity, and race) and baseline characteristics (height, weight, BMI, and renal function). Age will be calculated from the date of birth to the informed consent date and will be summarized as a continuous variable and categorized (18 to 45 years, > 45 to 65 years, > 65 to 75 years and > 75 years). Renal function will be categorized as normal (creatinine clearance [CrCl] > 80 mL/min), mild renal impairment (CrCl > 50 to 80 mL/min), moderate renal impairment (CrCl 30 to 50 mL/min) and severe renal impairment (CrCl < 30 mL/min). Creatinine clearance will be calculated from the local laboratory data and will be determined from the Cockcroft-Gault equation:

$$\frac{(140 - \text{age}[\text{yrs}]) * \text{weight} [\text{kg}] * (Z)}{\text{Cr} [\text{mg/dL}] * 72}$$

Z = 1.0, if Male
Z = 0.85, if Female

Differences between treatment groups will be analyzed using Fisher's exact test for dichotomous variables (gender, ethnicity, and race) and the Wilcoxon Rank Sum test for continuous variables (age, height, weight, and BMI).

The number and percentage of subjects with reported ABSSSI relevant medical history (relevant surgical procedure that resulted in the primary infection, recent trauma that resulted in the primary infection, iv drug abuse, prior ABSSSI, association of ABSSSI with chronic skin lesions, concurrent secondary ABSSSI lesions, diabetes mellitus [based on the MedDRA higher level term "Diabetes mellitus (incl subtypes)"], hepatitis C [based on the MedDRA preferred terms of "Hepatitis C" and/or "Chronic Hepatitis C"], infection result of vascular insufficiency or edema, and peripheral artery disease) will be summarized by treatment group for the mITT and CE-PTE populations. Differences between treatment groups in the percent of subjects with each relevant medical history will be determined using Fisher's exact test. Other medical and surgical history will be coded using MedDRA and summarized based on MedDRA system organ class and treatment group for the mITT and Safety populations. The number and percentage of subjects with a history of diabetes mellitus and hepatitis C will be presented by treatment group in the Safety population.

Listings will be provided of those subjects who were randomized to the wrong ABSSSI type of infection stratum and wrong prior antibiotic stratum. The type of infection listing will provide the subject ID, treatment group, randomized type of infection and actual (as recorded on the eCRF) type of infection. The prior antibiotic listing will provide the subject ID, treatment group, randomization date and time, randomized prior antibiotic stratum, preferred term of prior antibiotic, start and stop date/time of prior antibiotic, hours prior to randomization, dose and frequency of the antibiotic.

Descriptive statistics of the primary infection site will be provided for the mITT and CE-PTE populations. These include type of ABSSSI infection (cellulitis/erysipelas, major abscess, wound infection) and anatomical site (categorized as scalp, neck, face, chest, abdomen, back, groin, hand, foot, shoulder, buttock, axillary, arm, leg, elbow and knee). Lesion measurements (length, width and area of erythema, edema and/or induration, and for subjects with wounds and abscesses, the shortest measurement from peripheral margin), local signs and symptoms (tenderness, edema, erythema, induration, and drainage [none, serous/serosanguineous, seropurulent, and purulent]), and systemic signs (lymphadenopathy proximal to primary lesion site, presence of lymphangitis proximal to primary lesion site, WBC count $\geq 10,000$ cells/mm³ or ≤ 4000 cells/mm³, $\geq 15\%$ immature neutrophils, temperature [as a continuous variable and defined as fever/no fever at baseline $> 38.0^{\circ}\text{C}$, hypothermia $< 36.0^{\circ}\text{C}$]) will be summarized by treatment group. The percentage of subjects meeting the systemic inflammatory response syndrome (SIRS) criteria at baseline will also be provided (yes vs no). SIRS is defined as having 2 or more of the following criteria: temperature $< 36^{\circ}\text{C}$ or $> 38^{\circ}\text{C}$, heart rate > 90 bpm, respiratory rate > 20 bpm, or WBC count < 4000 cells/mm³ or $> 12,000$ cells/mm³ or $> 10\%$ bands. Descriptive statistics of baseline lesion area and a summary of the local signs and symptoms will also be provided by treatment group separately by type of ABSSSI infection (actual as recorded on the eCRF). Differences between treatment groups will be analyzed using Fisher's exact test for dichotomous variables and the Wilcoxon Rank Sum test for ordinal and continuous variables.

For those subjects with a concurrent secondary ABSSSI, a summary or listing (depending on the number of subjects with a concurrent secondary ABSSSI) of the lesion type and organisms isolated will be provided by treatment group.

9.2.1 Baseline Microbiology

The microbiological assessment of the primary ABSSSI site specimen by the local laboratory will be summarized by treatment group for the mITT population. A frequency distribution of the specimen collection method, the number and percentage of subjects with no growth and growth will be presented.

The pathogenic organisms identified from the baseline blood culture or culture of the primary ABSSSI site will be presented. The number and percentage of subjects with Gram-positive organisms (aerobes and anaerobes) and with Gram-negative organisms (aerobes and anaerobes) will be presented by genus and species for the micro-mITT and ME populations. The same pathogen identified from both the blood and the culture of the ABSSSI will be counted only once in the summary. In addition, the number and percentage of subjects with mono-microbial Gram-positive and poly-microbial infections (Gram-positive only and mixed infections (Gram-positive and Gram-negative) will be provided overall and by type of infection (micro-mITT population only)

The percentage of subjects with a positive blood culture by pathogenic organism will be provided for the micro-mITT and ME populations. The number and percentage of subjects with a Gram-positive organism (aerobes and anaerobes) and with a Gram-negative organism (aerobes and anaerobes) will be presented by genus and species.

A listing will be provided that includes all baseline and post-baseline isolates obtained from the blood and ABSSSI site specimen and will indicate the type of specimen and pathogenic organism.

Several tables providing minimum inhibitory concentration (MIC) data will be provided for the micro-mITT and ME populations:

- The MIC distribution to omadacycline and linezolid, across treatment groups
- The MIC distribution to the test article received, by treatment group
- MIC summary statistics (ie, range, MIC₅₀, and MIC₉₀) to the test article received. The MIC range will be provided for all baseline pathogens. The MIC₅₀ and MIC₉₀ will be provided only for those pathogens isolated at least 10 times in a treatment group.

The distribution of disk diffusion zone diameters (mm) will be provided for the test article received, by treatment group.

In all microbiology analyses, the following apply:

- If there are multiple specimens (of the same sample type) from the same time-point where the same pathogen is isolated, only the pathogen with the highest MIC to the test article

received will be used. If the pathogens have the same MIC to test article received, the one with the lowest accession number will be used. The Gram's stain associated with the selected pathogen will be utilized for analysis.

- If the same pathogen is identified from the blood and ABSSSI sample, for tables providing MIC or disk diffusion data, the pathogen with the highest MIC to the test article received will be used.
- MRSA and MSSA are considered distinct pathogens.
- Vancomycin susceptibility is provided for all *Enterococcus* spp. defined as pathogens. Vancomycin resistant and vancomycin susceptible isolates of each species are considered distinct pathogens (ie, vancomycin resistant *E. faecalis* and vancomycin susceptible *E. faecalis* are distinct)
- When per-subject counts of *Staphylococcus aureus* are presented, subjects with both MRSA and MSSA are counted only once.
- When per-subject counts of *Enterococcus* spp. pathogens are presented, subjects with both vancomycin susceptible and vancomycin resistant isolates of the same species are counted only once.

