6.1.4 Microbiological Modified Intent-to-Treat (micro-mITT) Population

The micro-mITT population will consist of all subjects in the mITT population who have at least one Gram-positive causative bacterial pathogen identified from a blood culture or from a culture of a microbiological sample obtained from the primary ABSSSI site at baseline using a valid sampling technique. Pathogen determination is based on the genus and species identification from the central laboratory. If the local laboratory grows an acceptable pathogen but the central laboratory is not able to grow the isolate, if isolates are lost during transportation or storage, or there are major discrepancies between the local and central laboratory in the identification of species, the central laboratory or other Sponsor designee will request that the local laboratory resend the isolate. If the central laboratory cannot determine the genus and species of the isolate for any reason, the local laboratory determination of genus and species will be used for pathogen identification. The central laboratory identification of genus and species is used for analysis unless no central determination exists in which case the local laboratory determination is used. If the central lab does not speciate the pathogen but the local/regional lab does speciate the pathogen, the Sponsor will make the final determination as to which pathogen identification is used for analysis.

An acceptable ABSSSI site specimen obtained via a valid sampling technique is defined as one obtained from a biopsy of involved cutaneous or subcutaneous tissue preferably from the advancing margin of the lesion, debrided tissue, tissue scraping (using curette or scalpel), needle aspirate of involved, nonpurulent cutaneous or subcutaneous tissue, pus or infected tissue collected during an incision and drainage procedure, pus aspirated into a syringe or a deep swab of purulent material (only if collected from infected tissue that has been incised or is draining). Surface swabs of wounds, inflamed skin or drainage (including purulent material) are not considered valid sampling techniques. If more than one baseline ABSSSI site sample was obtained using a valid sampling technique or more than one baseline blood sample was obtained, isolates from all samples will be reviewed for pathogen determination.

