Descriptive statistics of the primary infection site measurements (surface area [length x width]) will also be provided at each visit the infection site was measured for the mITT populations. The measurement at the visit, the absolute change from baseline, and the percent change from baseline will be provided at each visit. The percent change from baseline will be categorized as, $< 0\%$ (any increase), and decreases of 0 to $< 5\%$, 5 to $< 10\%$, 10 to $< 15\%$, 15 to $< 20\%$, 20 to $< 30\%$, 30 to $< 40\%$, 40 to $< 50\%$ and 50% to 100%.

All-cause mortality (ACM) at 30 days after randomization will be summarized in the ITT population. Subjects who are lost to follow-up will be excluded from this analysis.

Descriptive statistics of temperature will be provided for each visit temperature was measured for the mITT and CE-PTE population. The measurement at the visit and the absolute change from baseline will be provided at each visit, as will the percentage of subjects who have a temperature $\leq 37.8^{\circ}\text{C}$.

A concordance analysis of the primary efficacy outcome (Early Clinical Response at 48 to 72 hours) with the overall assessment of Clinical Response at the PTE Visit (based on the investigator's assessment) and the investigator's assessment of Clinical Response at the EOT Visit will be conducted in the mITT population. A concordance analysis of per-subject microbiological response and the investigator's assessment of Clinical Response at the EOT Visit will be conducted in the micro-mITT population.

For the micro-mITT and ME populations, the number and percentage of subjects with an Early Clinical Success (only micro-mITT population), with an assessment of Clinical Success (based on the investigator's assessment) at the EOT Visit (micro-mITT and ME-EOT populations) and an overall assessment of Clinical Success at the PTE Visit (based on investigator's assessment, micro-mITT and ME-PTE populations), will be tabulated by baseline MIC to omadacycline and linezolid by pathogen (for those pathogens occurring at least 5 times in one of the treatment groups) and treatment group.

Microbiological Outcomes

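### Where a subject has duplicate isolates of one pathogen, the isolate is chosen by the MIC to the drug received, so the both-drug MIC tables select isolates differently in each arm

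*SAP*

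**What the plan says.** SAP 9.2.1 introduces its conventions with "In all microbiology analyses, the following apply". Two of them choose among duplicate isolates.

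- **Several specimens of one sample type at one time-point, same pathogen:** "only the pathogen with the highest MIC to the test article" received is kept. Ties are settled as follows: "If the pathogens have the same MIC to test article received, the one with the lowest accession number will be used". The Gram's stain that belongs to the chosen isolate is the one analysed.
- **Same pathogen in blood and at the infection site:** "for tables providing MIC or disk diffusion data, the pathogen with the highest MIC to the test article received will be used".

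The planned outputs are of two kinds. Some concern only the drug taken: "The MIC distribution to the test article received, by treatment group", the MIC range, MIC50 and MIC90, the disk zones, and the decreasing-susceptibility analysis in SAP 10.4. Others present both drugs: "The MIC distribution to omadacycline and linezolid, across treatment groups" in SAP 9.2.1, and the SAP 10.4 tables in which clinical success "will be tabulated by baseline MIC to omadacycline and linezolid by pathogen" and treatment group. No separate selection rule is given for the second kind.

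On the population, SAP 6.1.4 states: "The micro-mITT population will consist of all subjects in the mITT population who have at least one Gram-positive causative bacterial pathogen". The mITT population (SAP 6.1.3) is drawn from all randomized subjects and does not require dosing.

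**The concern.** A baseline MIC table that covers both arms should choose isolates in the same way in both. Here the choice depends on treatment. In an omadacycline MIC table, an omadacycline-arm subject with duplicates contributes the highest omadacycline MIC. A linezolid-arm subject contributes the omadacycline MIC of whichever isolate had the highest linezolid MIC. The linezolid table has the mirror-image problem. Two arms with identical isolates would therefore show different MIC distributions, each drug looking less active in its own arm. Cells of the success-by-MIC tables would not be defined alike in the two arms.

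There is also a gap. An undosed subject can be in the micro-mITT population but has no test article received, so with duplicate isolates the rule does not say which one to keep.

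**Working it through.** **1. Which outputs are affected**

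| Output | Drug tabulated | Drug used to select | Consistent across arms? |
|---|---|---|---|
| MIC distribution, range, MIC50/MIC90, disk zones to drug received (9.2.1) | drug received | drug received | yes |
| Decreasing susceptibility (10.4) | drug received | drug received | yes |
| MIC distribution to both drugs (9.2.1) | both | drug received | no |
| Clinical success by MIC to both drugs (10.4) | both | drug received | no |

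Reading the both-drug distribution as pooled over arms does not remove the problem, because the pool then mixes two selection rules.

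**2. One subject (illustrative values).** Two baseline isolates of one pathogen have omadacycline/linezolid MICs of 0.12/2 and 0.5/1. In the omadacycline arm the second isolate is kept and the omadacycline table receives 0.5. In the linezolid arm the first is kept and the same table receives 0.12.

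**3. Size among subject-pathogens with duplicates.** The documents give neither the spread between duplicates nor the share of subjects with them, so the inputs are assumptions: two isolates, normal log2 MICs, within-subject SD σ = 0.5 to 1 doubling dilution, and correlation ρ = 0 to 0.9 between the two drugs' MICs within a subject. The true distributions are the same in both arms.

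- Mean excess of the larger of two values over the subject's own mean: σ/√π = 0.564σ.
- Mean excess in omadacycline MIC when the isolate is chosen by linezolid MIC: ρ × 0.564σ.
- Shift between arms: 0.564σ(1 − ρ).

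| σ | ρ = 0 | ρ = 0.5 | ρ = 0.9 |
|---|---|---|---|
| 0.5 | 0.28 | 0.14 | 0.03 |
| 1.0 | 0.56 | 0.28 | 0.06 |

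A simulation with MICs rounded to whole doubling dilutions and ties given to the first isolate (400,000 pairs per setting) gave 0.28, 0.18 and 0.09 for σ = 0.5, and 0.56, 0.30 and 0.10 for σ = 1. The two rules returned a different omadacycline MIC in 9% to 36% of pairs.

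**4. How often the gap is a full dilution.** In the unrounded model, two isolates differ by at least one dilution in omadacycline MIC with probability 2[1 − Φ(1/(σ√2))], which is 16% for σ = 0.5 and 48% for σ = 1. The isolate kept by linezolid MIC lies at least one dilution below the subject's highest omadacycline MIC less often. At ρ = 0 it does so in half of those cases (8% and 24%), at ρ = 0.5 in 2% and 11%, and at ρ = 0.9 in under 1%.

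**5. Size over all subject-pathogens.** Multiply the shift by the share f with duplicates (assumed 2% to 20%). With the rounded-model shifts of 0.09 to 0.56:

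- f = 2%: 0.002 to 0.011 dilutions.
- f = 10%: 0.009 to 0.056.
- f = 20%: 0.019 to 0.113.

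**6. After the change.** If both arms select on the drug being tabulated, the selection difference is zero by construction. The received-drug tables do not change.

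**The case against.** The case for leaving the text alone has several parts.

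- **Narrow reach.** Most planned MIC outputs concern the drug received, and for these the rule is right. Selection is per pathogen per subject, and a subject with a single isolate of each pathogen is unaffected. This stands.
- **Descriptive tables.** SAP 10.4 says its intervals are descriptive and support no non-inferiority conclusion, and no test is planned on the MIC tables. This stands.
- **Use of the treatment code.** The rule is deterministic with a fixed tie-break, and SAP 6.2.2 already allows programmatic derivation after unblinding for population criteria that need actual treatment. So dependence on the code is not a fault in itself. The fault is that the dependence enters tables covering both arms.
- **Undosed subjects.** The gap needs an undosed subject with duplicate isolates. Protocol 11.1 plans the first dose on site within 4 hours of randomization, and the ME populations require dosing. The gap is real but marginal.

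A reader might infer that the trial relies on the linezolid arm as a control for whether omadacycline MIC predicts response to omadacycline specifically. Neither document gives it that role. The stated exposure-response work (Protocol 22.12) uses omadacycline exposure and AUC/MIC, and for omadacycline-treated subjects the rule already picks the highest omadacycline MIC. It would also be wrong to infer that every subject's MIC data, or the efficacy conclusions, depend on the treatment code.

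None of this supplies a selection rule for the two both-drug outputs. Duplicates are foreseeable: Protocol 16.1.3.3 asks for two baseline blood-culture sets from independent sites, and SAP 6.1.4 anticipates more than one infection-site sample.

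**Conclusion.** The point holds, and it is minor. Followed as written, SAP 9.2.1 selects duplicate isolates by a different drug in each arm for the both-drug MIC distribution and the success-by-MIC tables. The bias has a fixed direction: each drug's MICs are raised in its own arm. Under the assumptions above it is about 0.03 to 0.56 doubling dilutions among subject-pathogens with two isolates. Over all subject-pathogens it is roughly 0.1 or less if up to 20% have duplicates, and the top of that range needs σ = 1 and ρ = 0. The size is uncertain because none of these inputs is in the documents; the direction follows from the rule and needs only that the two drugs' MICs do not rank the duplicates identically. The primary Early Clinical Response analysis and the non-inferiority conclusion do not depend on the rule.

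**What to change.** Add one sentence to SAP 9.2.1: for tables that present MICs to both drugs, or outcome by MIC to both drugs, use the isolate with the highest MIC to the antibacterial being tabulated, identically in both arms and for undosed subjects. Keep the received-drug rule for the received-drug MIC and disk tables and for the decreasing-susceptibility analysis. For the Gram's stain and other outputs with no single tabulated drug, use one rule that does not depend on treatment, such as the lowest accession number. Substituting the new phrase throughout the existing bullets would not work, because outputs that tabulate no drug would then have no selected isolate.

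The cost is a short SAP edit and a small programming change. No new data are needed, since Protocol 17.3 already plans central MIC testing to both drugs for the submitted isolates. Selection for the both-drug tables could then be fixed before unblinding. The small downside is that a subject's two MICs may come from different isolates in different tables, which a footnote can state.
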